The expected	The screening period from signing the informed consent form to enrollment is expected to be 4 weeks, the treatment period is 1~8 weeks, and the short-term follow up after the last treatment are divided into
the	short-term follow-up and long-term follow-up, and the maximum duration
unc narticinant's	of expected participation of each subject from screening to the end of short-term
participation	follow-up is 12 weeks +3 months. Long-term follow-up continued after the end of the
participation	short-term follow-up until the fifth year after the end of the last radiotherapy.
Expected	The first subject is expected to be enrolled in December 2021, and the clinical trial
overall	institution expects to enroll 8-18 subjects per month, for a total enrollment time of
duration of	about 4 months, and the last 1 subject ends the trial (short-term follow-up) is End In
clinical trials	September 2022, the overall duration of the clinical trial included all working
and long-term	hours before, during and after the start of all clinical trials, and the overall duration of
follow-up	the clinical trial was 16 months.

Protocol summary

	The first subject is expected to start long-term follow-up in May 2022 and the last		
	one subject to end long-term follow-up in June 2027, and the overall duration		
	of long-term follow-up in clinical trials includes all clinical runs, After all working		
	hours ended, the total long-term follow-up period for clinical studies was		
	approximately 62 months.		
	Disease Control Rate (DCR).		
	Evaluation time: 3 months ± 7 days after the last treatment.		
	Definition of indicators: Complete Response (CR), Partial Response (PR), Stable		
	Disease (SD) for disease control; No biochemical recurrence at the end of prostate		
D .	cancer treatment, no regional lymph nodes or distant metastases, considered disease		
Primary	control. Proportion of participants who developed disease control three months after		
effectiveness	the end of the last radiotherapy. Participants who discontinued the trial for any reason		
Evaluation	(except loss to follow-up) before the end of radiation therapy were considered to have		
indicators	progression (PD) or uncontrolled.		
	Evaluation methodology: Response Evaluation Criteria in Solid Tumors RECIST		
	Version 1.1 (RECIST 1.1) by an independent imaging review team Changes in		
	tumour CT or MRI imaging before and after treatment were assessed. At 3 months		

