3.1.2 Choice of trial method and justification

This trial was designed using the prospective, two-center, single-group target value method.

- (1) Prospective study: Adopt a research approach that traces from the present to the future. Prospective studies can establish cause and effect; There are unified diagnosis, detection and evaluation standards for the obtained data, so the data processing is controllable.
- (2) Two centers: Select 2 clinical trial institutions to carry out the clinical trial. More cases than single-center trials can be obtained in the same amount of time, thus shortening the duration of clinical trials.
- (3) Single-group target value method: Because the same device of the experimental medical device is radioactive and difficult to obtain, the existing treatment method is not feasible due to objective conditions, so the single-group target value method is adopted. Moreover, the applicable population and main evaluation indicators of experimental medical devices can be fully defined and relatively stable; The main evaluation index adopts the effective rate mentioned in the "Guidelines for the Technical Review of Clinical Evaluation of Proton Carbon Ion Therapy System" (CFDA Circular No. 4 [2018]), which is relatively objective and reproducible. According to the Guidelines for the Technical Review of Clinical Evaluation of Proton Carbon Ion Therapeutic response rate for experimental medical devices should be at least 80%, and the expected value should be 95%. Among them, the effective definition is: CR+PR+SD (complete response CR, partial response PR, disease stable SD), which is basically consistent with the definition of tumor disease control rate in this clinical trial. Therefore, no control group was set up in this clinical trial, and the single-group target value method was used to evaluate whether the tumor disease control rate reached the target value (80%) and the main safety evaluation index CTCAE 3 when ProBeam was used in

radiotherapy for tumor patients Whether the proportion of grade toxicities is less than acceptable (5%) and whether the proportion of CTCAE grade 4 and 5 toxicities is acceptable (0%).

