Evaluation method: The changes in tumor CT or MRI imaging before and after treatment were evaluated by an independent imaging review panel according to RECIST 1.1. At 3 months of radiographic evaluation, if PD is found, PET-CT is required to confirm it.

Calculation formula: DCR = number of disease control subjects / total number of subjects × 100%.

Criteria: See RECIST 1.1 for details. At the time of 3-month imaging evaluation, if the patient is found to have PD, PET-CT examination is required to confirm it, if progress is confirmed, it is recorded as PD, if progress cannot be confirmed, it may be false progression, and it is recorded as SD. If prostate cancer does not have biochemical recurrence, PET-CT examination is not required, and there is no metastasis by default, which is regarded as tumor control, and if biochemical recurrence occurs, it is regarded as tumor not controlled, and PET-CT is required to confirm tumor metastasis.

Note: Participants who aborted the trial for any reason (except loss to follow-up) before the end of the last radiation therapy were considered to have disease progression (PD) or were not controlled. Disease site evaluation uses the same approach as baseline, including consistent contrasted/non-contrast scans and prompt scanning. If changes are needed, the case must be discussed with a radiologist to determine whether an alternative approach is possible. If not, the objective situation in the future is unclear.

3.1.4.2 Secondary effectiveness evaluation indicators and their methods and timing of evaluation, recording, analysis

(1) Objective response rate (ORR).

Reason for selection: The Guidelines for the Review of Clinical Evaluation Technologies of Proton Carbon Ion Therapy Systems (CFDA Circular No. 4 [2018]) recommends the use of the latest version of the commonly used evaluation criteria for radiation oncology as the clinical trial evaluation criteria, so RECIST 1.1 is used Relevant indicators as effectiveness evaluation criteria; Due to the particularity of the disease, the evaluation method recommended in the relevant diagnosis and treatment guidelines is selected. All of them can directly measure the effect of radiotherapy and are widely recognized and applied by clinicians.

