4.2 Sample size calculation

4.2.1 Total sample size

This clinical trial intends to enroll 47 subjects. The sample size determination process is as follows:

This clinical study is designed for clinical verification of a single group of target values, and the tumor disease control rate, the main effectiveness evaluation index, is used as the basis for sample size estimation. According to the Guidelines for the Review of Clinical Evaluation Technologies of Proton Carbon Ion Therapy System (CFDA Circular No. 4 of 2018), the target value is set at 80%, and the bilateral significance level is 0.05, and the power degree 80%, applying the sample size estimation professional software PASS 15.0, calculated by the above parameters, the test group needs a sample size of at least 42 cases. Considering that about 10% of cases may be dropped or lost to follow-up during clinical validation, the sample size of the experimental group was expanded to 47 cases.

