4.3 The level of significance and power of clinical trials

The significance level α (bilateral) = 0.05, and the power was 80%.

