- (3) The missing values of DCR and primary safety evaluation indicators
 (proportion of CTCAE grade 3 toxicities, proportion of CTCAE grade
 4 and 5 toxicities) at 3 months after the end of treatment can be estimated using worst-case scenarios.
- (4) The missing values of qualitative secondary effectiveness evaluation indicators ORR, DCR and long-term follow-up effectiveness evaluation indicators can be estimated using worst-case scenarios;
- (5) The missing values of quantitative secondary efficacy evaluation indicators DOR, tumor markers, product ease assessment and long-term follow-up effectiveness evaluation indicators were not estimated.
- (6) Erroneous, unreasonable data (out-of-range data and data that contradicts other data or indicators of the study protocol) can be treated as missing values;
- (7) Worst-case estimates are used for missing values for all minor safety indicators;

- (8) The sensitivity analysis of the main effectiveness evaluation indicators and main safety evaluation indicators after treatment was carried out in the whole analysis center.
- (9) The sensitivity analysis of all secondary effectiveness evaluation indicators after treatment was carried out in the whole analysis center.
- (10) For all secondary safety evaluation indicators after treatment, sensitivity analysis was carried out in the security dataset.

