4.3 Effectiveness indicators are missing

When analysing the main effectiveness evaluation indicators based on PPS, it is not necessary to consider filling them.

In the sensitivity analysis of the main effectiveness evaluation indicators based on FAS, the missing values of the main effectiveness evaluation indicators were not filled.

The missing values of qualitative secondary effectiveness evaluation indicators ORR and DCR were filled by the method of worst observational data carryover (WOCF).

The missing value of the quantitative secondary effectiveness evaluation index DOR was not filled.

Other secondary effectiveness evaluation indicators, such as tumor markers, tumor-specific symptoms, and

Confidential Information Page 9 / 17

rsion: V1.0 Date: 2022-11-11

product ease of use, were not filled.

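### A subject lost to follow-up during radiotherapy is exempt from the failure rule and drops out of the deciding analysis set; as the per-protocol set is defined, mid-course withdrawals may drop out too

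*Protocol*

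**What the plan says.** **The failure rule and its exemption.** The Note to the primary endpoint, disease control rate (DCR) at 3 months (protocol 3.1.4.1), says that subjects who abort the trial "for any reason (except loss to follow-up) before the end of the last radiation therapy were considered to have disease progression (PD" or not controlled. The protocol summary has the same carve-out: "except loss to follow-up) before the end of radiation therapy were considered to have" progression or no control. Parallel notes with the same exemption stand under objective response rate (ORR) and 1-month DCR (3.1.4.2) and under tumor recurrence (3.1.5.2). None gives a reason for it.

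**The deciding set.** Protocol 4.9 and SAP 3 make the PPS the main population for effectiveness. It requires a measurable lesion at baseline and at least one completed post-baseline assessment of the primary indicator. SAP 5.6 lets the PPS prevail if the FAS and PPS conclusions differ.

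**Missing primary outcomes.**
- Protocol 4.7.2 item (3) says missing values of DCR and of the main safety indicators (the last being grade "4 and 5 toxicities) at 3 months after the end of treatment can be estimated using worst-case scenarios").
- SAP 4.3: "When analysing the main effectiveness evaluation indicators based on PPS, it is not necessary to consider filling them". The same section says missing values are not filled in the FAS sensitivity analysis either.
- SAP 5.4.1 says they are filled in that analysis, by worst observation carried forward (WOCF).

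**The SAP endpoint.** SAP 2.1.1 defines DCR without the early-stopper rule. SAP 6, which lists changes from the protocol's analysis, does not mention dropping it.

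**The concern.** Someone who stops attending part-way through the course has not completed treatment with the device, whether or not the site can still reach them. The protocol treats stopping early as failure, then excuses the stoppers about whom least is known. Such a subject has no completed primary assessment, because response imaging is scheduled at 1 and 3 months after the last treatment. They leave the PPS and are not counted against the device in the analysis that prevails.

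The gap may be wider than the exemption. A subject who withdraws mid-course has normally completed no primary assessment either, and the PPS definition has no exception for subjects scored by rule. If that definition is applied as written, the protocol's failure rule does nothing in the main analysis. If the Note is given effect instead, withdrawn subjects stay as failures and lost subjects go, so the recorded reason for leaving decides between the two.

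Both readings favour the device, and the pass margin is a handful of subjects.

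**Working it through.** **Inputs.** Target: "the target value is set at 80%, and the bilateral significance level is 0.05" (protocol 4.2.1). Expected rate: "and the expected value should be 95"% (3.1.2). Power 80% (4.3). Dropout about 10% (4.2.1, 4.4). Pass rule: lower two-sided 95% Clopper-Pearson limit above 80% (4.5, 4.7.1).

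**1. The plan's own figure.** With p0 = 0.80 and p1 = 0.95,

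n = [(z0.975·√(p0(1−p0)) + z0.80·√(p1(1−p1))) / (p1−p0)]²
= [(1.960 × 0.4000 + 0.8416 × 0.2179) / 0.15]² = 41.59, rounded up to 42.

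Then 42/0.90 = 46.7, so 47. Both figures reproduce.

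**2. Failures allowed.** Clopper-Pearson lower limits:

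| n analysed | 3 failures | 4 failures |
|---|---|---|
| 42 | 39/42: 80.5% | 38/42: 77.4% |
| 43 | 40/43: 80.9% | 39/43: 77.9% |
| 44 | 41/44: 81.3% | 40/44: 78.3% |
| 45 | 42/45: 81.7% | 41/45: 78.8% |
| 46 | 43/46: 82.1% | 42/46: 79.2% |
| 47 | 44/47: 82.5% | 43/47: 79.6% |

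Three failures pass and four fail at every n. Excluding a stopper leaves the allowance intact; counting one uses a third of it.

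**3. Effect on one data set** (47 treated, all otherwise PPS-eligible; stopper numbers are assumptions):

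| Stoppers | Other failures | Counted as not controlled | Excluded |
|---|---|---|---|
| 1 | 3 | 43/47: 79.6%, fail | 43/46: 82.1%, pass |
| 2 | 2 | 43/47: 79.6%, fail | 43/45: 84.9%, pass |
| 4 | 0 | 43/47: 79.6%, fail | 43/43: 91.8%, pass |

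**4. Effect on the chance of passing.** With k stoppers, the other 47−k controlled at a true rate of 95%, and X their number controlled: if stoppers are excluded, passing needs X ≥ 44−k; if they are counted, X ≥ 44.

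| k | Excluded | Counted |
|---|---|---|
| 0 | 79.3% | 79.3% |
| 1 | 80.3% | 59.4% |
| 2 | 81.3% | 33.5% |
| 3 | 82.4% | 10.5% |
| 4 | 83.3% | 0% |
| 5 | 84.3% | 0% |

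The range 1 to 5 runs up to about the plan's 10% dropout allowance (47 × 0.10 = 4.7).

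**5. Effect on false passes.** Take k = 3 and 85% control in the other 44. With every stopper scored as a failure, expected DCR is 44 × 0.85/47 = 79.6%, below target. Excluding the stoppers gives a pass probability of 8.7%; counting them gives 0.1%.

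**6. What the text does with each type of stopper.**

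| | PPS, definition read literally | PPS, Note given effect | FAS |
|---|---|---|---|
| Withdrew mid-course | out | failure | failure under the Note, but SAP 2.1.1 omits it |
| Lost mid-course | out | out | unfilled (SAP 4.3) or WOCF (SAP 5.4.1) |

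**The case against.** **The protocol need not contradict itself.** The Note can be read as scoring known discontinuations by definition and leaving loss to follow-up to the missing-data rule in 4.7.2(3), where worst case also means not controlled. That is a fair reading of the intent. But 4.7.2(3) is only permissive, and SAP 4.3 does no filling in the PPS, so the intent does not reach the deciding analysis.

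**A reader might infer that the recorded reason always decides a mid-course stopper's fate.** The documents do not establish this. It requires a withdrawn stopper to sit in the PPS as a failure, and the literal PPS definition excludes that subject too. The reason decides only where the Note is given effect.

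**A reader might infer that a lost subject is not a failure in any SAP analysis.** That is also unsupported. DCR is defined over the total number of subjects, so an unfilled FAS subject may stay in the denominator and count as not controlled. WOCF may also draw on unscheduled data (SAP 4.1). What stands is that no SAP text clearly makes the subject a failure: SAP 4.3 and 5.4.1 disagree, and WOCF may have no post-treatment scan to carry.

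**A reader might suspect that reasons would be coded to suit the result.** Nothing in the documents shows this. An independent panel reads the images, and exclusions are settled at a data review meeting before lock (SAP 5.3.2). The problem lies in the rule, whoever applies it.

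**The reversal is conditional.** With one stopper it needs exactly three failures among the other 46. At a true rate of 95% that has probability 80.3% − 59.4% = 20.9%, given that such a subject exists. Loss during a scheduled course of visits may well be rare. This limits the expected impact but does not remove the gap.

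**Conclusion.** The concern holds in this form. A subject lost to follow-up before the end of radiotherapy is exempt from the failure rule and leaves the PPS, which prevails. Read literally, the PPS definition also removes mid-course withdrawals, so the protocol's failure rule may be without effect in the main analysis. Treatment of these subjects in the FAS is undetermined.

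Because only three failures are allowed, one such subject reverses the primary conclusion when there are exactly three others. The size rests on assumptions: all 47 are otherwise PPS-eligible, the rest have a true rate of 95%, and the number of stoppers is illustrative. The documents give no expected number of mid-course losses, so the unconditional effect cannot be stated. The plan should be corrected, because a rare event can decide the trial and the text does not settle how it is scored.

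**What to change.** Four linked changes, settled before database lock. The first alone would not work, because the PPS definition would still remove the subject.

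1. In the protocol summary and 3.1.4.1, delete the loss-to-follow-up exception for exits before the end of radiotherapy. Do the same in the ORR, 1-month DCR and recurrence notes so that the endpoints stay aligned.
2. Copy the rule into SAP 2.1.1.
3. Add to the PPS definition (protocol 4.9, SAP 3) that otherwise eligible subjects scored as not controlled by this rule remain in the PPS as failures without a completed assessment.
4. Reconcile SAP 4.3 with 5.4.1 so that a missing 3-month DCR in the FAS is set to not controlled, in line with protocol 4.7.2(3).

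Loss to follow-up after completed radiotherapy stays under the missing-data rule.

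**Cost.** A few sentences in each document, and power. Each such subject uses one of the three permitted failures; one lowers the pass probability from 80.3% to 59.4% under the assumptions above. The 10% allowance does not protect against this, since it budgets for subjects removed from the analysis. If enrolment is still open, a 48th subject would offset one stopper: 44/48 has a lower limit of 80.02%, so four failures would pass, and with one of them the stopper the trial needs at least 44 of the other 47, probability 79.3% at a true rate of 95%.

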	of radiographic evaluation, if PD is found, PET-CT is required to confirm it.		
	(1) Common Terminology Criteria for Adverse Events (CTCAE) Grade 3 toxicity		
	ratio		
	Evaluation time: 3 months \pm 7 days after the end of the last treatment.		
	Indicator definition: Proportion of subjects with grade 3 toxicity during the		
	trial cycle.		
The main	Evaluation methodology: Investigators recorded AEs that occurred during the		
safety	clinical trial cycle and graded them according to CTCAE V5.0.		
evaluation	(2) CTCAE grade 4 and 5 toxicity ratio		
index	Evaluation time: the entire clinical trial cycle.		
	Indicator definition: Proportion of subjects with toxicity of grade 4 and 5 during		
	the trial cycle.		
	Evaluation methodology: Investigators recorded AEs that occurred during the		
	clinical trial cycle and graded them according to CTCAE V5.0.		
	(1) Objective Response Rate (ORR) (1 month \pm 7 days, 3 months, \pm 7 days after the		
	end of the last treatment).		
	(2) Duration of Response (DOR) (3 months ± 7 days) after the end of the last		
	treatment		
Secondary	(3) DCR (1 month ± 7 days after the end of the last treatment).		
effectiveness	(4) Tumor markers (if required) (screening period, 1 month ± 7 days, 2 months ± 7		
Evaluation	days, 3 months=7 after the end of the last treatment days).		
indicators	(5) Tumor-specific symptoms (screening period, 1 month ± 7 days, 2 mon ths ± 7 days,		
	3 months≠7 days).		
	(6) Product usability evaluation (ProBeam system, radiotherapy management software		
	(OIS), radiotherapy planning software (Eclipse)) (the day of completion of the last		
	treatment).		

	(1) CTCAE grade 1 and 2 toxicity ratio (3 months \pm 7 days after the end of the last
	treatment).
	(2) Laboratory tests [screening period, treatment period on the 1st day of each week
	(Monday to Sunday is considered as 1 calendar week, the day of the first treatment
	of each natural week) before treatment or -1 day, 3 days after the end of the last
	treatment, 1 Months ± 7 days, 2 months ± 7 days, 3 months ± 7 days].
Secondary	(3) Eastern Cooperative Oncology Group (ECOG) physical status grading [screening
safety	period, treatment period 1st day of each week (Monday to Sunday is regarded as 1
Salety	natural week, On the day of the first treatment of each calendar week) before or -1
indicators	day before treatment, within 3 days after the end of the last treatment, 1 month±7
mulcators	days, 2 months≠ days, 3 months ≠ days].

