Definition of indicators: CR or PR after the end of treatment is considered objective remission, prostate cancer has no biochemical recurrence at the end of the last treatment, and no regional lymph nodes or distant metastasis are considered objective remission. Proportion of participants who experienced objective remission at each time point after the end of the last treatment.

Metric type: Qualitative.

Data collection time: screening period, 1 month \pm 7 days, 3 months, \pm 7 days after the end of the last treatment.

Evaluation time: 1 month \pm 7 days, 3 months, \pm 7 days after the last treatment.

Site of evaluation: Tumor receiving radiation therapy.

Evaluation method: The changes in tumor CT or MRI imaging before and after treatment were evaluated by an independent imaging review panel according to RECIST 1.1. At 3 months of radiographic evaluation, if PD is found, PET-CT is required to confirm it.

Calculation formula: ORR = number of subjects in objective response / total number of subjects × 100%.

Criteria: See RECIST 1.1 for details. At the time of 3-month imaging evaluation, if the patient is found to have PD, PET-CT examination is required to confirm it, if progress is confirmed, it is recorded as PD, if progress cannot be confirmed, it may be false progression, and it is recorded as SD. If prostate cancer does not have biochemical recurrence, PET-CT examination is not required, and there is no metastasis by default, which is regarded as objective remission, and if biochemical recurrence occurs, it is regarded as not objectively remission, and PET-CT is required to confirm tumor metastasis.

Note: Participants who aborted the trial for any reason (other than loss to follow-up) before the end of the last radiotherapy were considered to have not responded objectively. Disease site evaluation uses the same approach as baseline, including consistent contrasted/non-contrast scans and prompt scanning. If changes are needed, the case must be discussed with a radiologist to determine whether an alternative approach is possible. If not, the objective situation in the future is unclear.

(2) Time to sustained remission (DOR).

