Reason for selection: The Guidelines for the Review of Clinical Evaluation Technologies of Proton Carbon Ion Therapy Systems (CFDA Circular No. 4 [2018]) recommends the use of the latest version of the commonly used evaluation criteria for radiation oncology as the clinical trial evaluation criteria, so RECIST 1.1 is used Relevant indicators as effectiveness evaluation criteria; Due to the particularity of the disease, the evaluation method recommended in the relevant diagnosis and treatment

guidelines is selected. They are all commonly used indicators for the evaluation of tumor treatment effects, and are widely recognized and applied by clinicians.

Indicator definition: the time between the first assessment of the tumour as CR or PR and the time between the first assessment of PD or death from any cause.

Indicator type: quantitative.

Data collection time: 1 month \pm 7 days, 3 months, \pm 7 days after the end of the screening period, until tumor progression or subject death.

Evaluation time: 3 months \pm 7 days after the last treatment.

Site of evaluation: Tumor receiving radiation therapy.

Evaluation method: The changes in tumor CT or MRI imaging before and after treatment were evaluated by an independent imaging review panel according to RECIST 1.1. At 3 months of radiographic evaluation, if PD is found, PET-CT is required to confirm it.

Calculation formula: DOR = time to death from PD or any cause on the first assessment - time to CR or PR for the first assessment;

Criteria: See RECIST 1.1 for details. At the time of 3-month imaging evaluation, if the patient is found to have PD, PET-CT examination is required to confirm it, if progress is confirmed, it is recorded as PD, if progress cannot be confirmed, it may be false progression, and it is recorded as SD.

Note: If no tumor progression or death is observed during the follow-up period after the end of radiotherapy, the formula is: DOR > last visit time after the end of the last radiotherapy - CR or PR time for first assessment. Others are the same as ORR.

(3) Tumor disease control rate (DCR).

Reason for selection: DCR 3 months after the end of the last treatment was the primary evaluation index, and DCR at other follow-up time was used as a secondary evaluation index.

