4.7.1 Data statistical methods

Statistical analysis with SAS 9.4 software.

All data are described statistically, including demographics, baselines, all efficacy measures, and all safety data. The measurement data give the mean, standard deviation, minimum, maximum, median, 25th quantile and 75th quantile; The counting data gives the frequency and the corresponding percentage.

Effectiveness Analysis:

The number and percentage of cases achieving DCR were calculated, and the Clopper-Pearson method was used to calculate the 95% confidence interval for tumor disease control rate. ORR was calculated and the Clopper-Pearson method was used to calculate the objective response rate 95% confidence interval. Descriptive statistics on the percentage change from baseline of the sum of the longest diameter (SLD) of the measurable tumor. The Waterfall Chart was made by the maximum percentage reduction in SLD per patient compared to the screening period.

The *Kaplan-Meier* method was used to calculate the median duration of response, median progression-free survival, median survival, and overall survival, and plotted *K-M* curves (long-term follow-up data).

For tumor markers, compare and evaluate the changes before and after treatment, and give clinical evaluation [no clinical significance, clinically significant (tend to normal), clinically significant (tend to be abnormal), not checked].

Safety Analysis:

Descriptive statistics were used to classify organ systems in MedDRA medical terms, and the incidence, occurrence, and severity of adverse events, adverse reactions, and serious adverse events were summarized.

Laboratory indicators, ECOG physical status classification and other safetyrelated indicators were compared and evaluated before and after treatment, and clinical evaluation ([no clinical significance, clinically significant (tending to normal), clinically significant (tending to abnormal), not checked], CTCAE grade evaluation before and after treatment cross-table.

4.7.2 Missing, unused, or erroneous data (including mid-exit and evacuation) and unreasonable data

All missing, unused or erroneous data (including mid-exit and withdrawal) and unreasonable data will be discussed and finalized by investigators and biostatisticians during the blinding review phase. The basic statistical principles of these data processing are as follows:

- (1) Describe the details of each shedding case;
- (2) Missing data from baseline, which can not be estimated;

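### Duration of response for event-free responders ends at the last visit, not the last tumour assessment, so individual durations can be overstated (low priority)

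*Protocol*

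**What the plan says.** Protocol section 3.1.4.2 (2) starts DOR at the first assessment of CR or PR and ends it at "the time between the first assessment of PD or death from any cause". The means of detection is imaging: "The changes in tumor CT or MRI imaging before and after treatment were evaluated by an independent imaging review panel according to RECIST 1.1".

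The Note in the same item covers subjects without an event. "If no tumor progression or death is observed during the follow-up period after the end of radiotherapy", the value is "DOR > last visit time after the end of the last radiotherapy - CR or PR time for first assessment". This is the only rule in either document for an event-free responder.

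The response schedule is given under ORR, item (1) of the same section: "Evaluation time: 1 month \pm 7 days, 3 months, \pm 7 days after the last treatment". DOR's own data collection times are also 1 and 3 months. Subjects are seen at 2 months as well: the protocol summary lists "Tumor markers (if required) (screening period, 1 month ± 7 days, 2 months ± 7" days, and the 2-month visit also has symptoms, laboratory tests and ECOG status. No response imaging is listed there.

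In protocol section 4.7.1 the Kaplan-Meier method "was used to calculate the median duration of response, median progression-free survival, median survival, and overall survival", marked as long-term follow-up data. The SAP covers short-term follow-up only. It gives the event formula for DOR (2.1.2), leaves missing DOR unfilled (4.3) and describes DOR without a censoring rule (5.4.2).

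**The concern.** A lower bound on duration is valid only up to the date to which response was verified. Except where death occurs, what ends a response is an assessed progression. A visit without an assessment says nothing about tumour status, yet the Note extends the duration to that visit.

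Two things are at stake. In short-term reporting, some listed durations would claim response over time in which the tumour was not assessed. In the long-term analysis, which has no plan among the supplied documents, the Note is the only censoring rule available to import. A subject censored at a scanless visit can then stay in the risk set at times when others' progression is being detected.

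**Working it through.** The documents state no figure for DOR, so there is none to reproduce. The sample size (42, raised to 47) rests on the disease control rate and is not affected.

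**Individual durations, short term.** Take a month as 365.25/12 = 30.44 days and a window of ±7 days on each date, so a gap between two dates varies by ±14 days. Excess = last visit date − last tumour assessment date.

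- Scan at month 1, last visit at month 2: 30.4 days, range 30.4 − 14 = 16.4 to 30.4 + 14 = 44.4.
- Scan at month 1, month 3 attended without a scan: 60.9 days, range 46.9 to 74.9.
- Last visit is month 3 with its scan: 0.

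The two scans are about 61 days apart, so the first case credits about half of the longest duration observable in this phase.

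**Individual durations, long term.** Section 2.2 gives 11 visits, and tumour outcomes are summarised at 6 months, 1, 2 and 5 years. If scans were done only at those times (an assumption), the excess could reach just under 3, 6, 12 and 36 months in the successive intervals. If every visit has a scan, it is 0.

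**Kaplan-Meier, common scan times, all scans done.** Censoring between two scans removes nobody from the risk set at either scan, so the last-visit and last-scan rules give the same curve. A simulation with assumed scans at 1, 3, 6, 12, 24 and 60 months, extra visits, true median DOR of 12 to 36 months and 5 to 20% yearly dropout gave identical estimates to three decimals.

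**Kaplan-Meier, visits without scans.** Suppose n responders are at risk at a scan time. A share f make their final visit then without a scan, and a share q of those scanned show progression. Assume missing the scan is unrelated to progression.

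- Last visit: all n stay at risk, so the curve is multiplied by 1 − (1 − f)q.
- Last scan: only (1 − f)n are at risk, so it is multiplied by 1 − q.
- Difference: fq. For assumed f = 5 to 15% and q = 10 to 30%, this runs from 0.05 × 0.10 = 0.5 points to 0.15 × 0.30 = 4.5 points.

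**Kaplan-Meier, wider check.** The DOR clock starts at month 1 or month 3 and visits have windows, so scan times are not exactly common on the DOR scale. A second simulation used an assumed schedule, true median 18 months and 10% yearly dropout. True response at 24 months is 0.5^(24/18) = 0.397, or 40%.

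| Assumed scenario | Last visit | Last scan | True |
|---|---|---|---|
| Random dropout | 42% | 39% | 40% |
| 10% of scans missed | 45% | 41% | 40% |
| Dropout related to progression | 50% | 45% | 40% |

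The rules differ by 3, 4 and 5 points. Under the last-scan rule 45 − 40 = 5 points of error remain when dropout is informative.

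**The case against.** The strongest objection is to a wider claim that a reader might infer: that the rule in general biases the Kaplan-Meier curve and median DOR upward. The documents do not support that. A responder scanned at month 1 and last seen at month 2 crosses no scan time. Nor, if scans occur only at the summary times, does one scanned at 2 years and last seen at 4.5 years. The second subject's censored value is 2.5 years longer, but the curve does not move through progression. In one assumed set-up with staggered response, all scans done and random dropout, the last-visit rule was the closer one (0.275 to 0.280 against a truth of 0.281, with 0.251 to 0.274 for last scan). In another check the median moved by under 0.2 month. This objection stands.

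These points also stand:

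- The long-term scan calendar is not in the supplied text, and the 6-month to 5-year points are reporting milestones.
- The Note belongs to the short-term endpoint, so its use in the long-term Kaplan-Meier analysis is an inference.
- Nothing in the documents says that subjects who do poorly stop imaging. Moving the censoring date would not remove informative dropout.
- For prostate cancer, status is biochemical, so markers taken at 2 months can count as an assessment.

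Two defences do not settle the matter. The greater-than sign makes the value a lower bound, but still one placed beyond the last verified date. Last visit may have been meant as the last DOR evaluation, since DOR's own collection times are 1 and 3 months. The text does not say so, and the fix would then merely state what was intended. Missed assessments are also foreseen: section 4.4 counts missing key evaluation data among the reasons for the 10% shedding rate.

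**Conclusion.** The point holds for individual durations. As written, the Note overstates a DOR lower bound by about 1 month (16 to 44 days) or about 2 months (47 to 75 days) in the two short-term situations shown. It overstates nothing when the last visit includes the assessment.

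For the long-term curve the point is conditional. If the same rule is used, and subjects attend without scans or leave after undetected progression, the overstatement is a few percentage points under the assumed inputs. With common scan times and complete scanning it is essentially nil. The long-term scan schedule, the missed-scan share and the dropout pattern are all assumptions.

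This is low priority. DOR is a secondary endpoint, and section 4.5 gives it no part in the pass/fail decision.

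**What to change.** Change the Note in protocol section 3.1.4.2 (2) so that responders without progression or death are censored at the date of their last evaluable tumour assessment. For prostate cancer, this is the last assessment of biochemical or metastatic status. Carry the sentence into the long-term analysis plan. Use the same date for long-term PFS, for which the supplied text states no censoring date, and use last contact only for OS.

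The cost is one sentence, using assessment dates that the trial already needs. No sample size or primary result changes. Reported DOR becomes slightly shorter. The last-scan rule is not closer to the truth in every scenario, and it reduces bias from informative dropout without removing it. Its merit is that every reported duration then rests on an assessed tumour status.
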